7.2 Handling of missing data and outliers

7.2.1 Missing data analysis methods

For analyses relating to the Weekly Mean Worst Itching Intensity NRS score, Skindex-10 Total Score and 5-D Itch Total Score, missing data will be imputed using a multiple imputation (MI) approach. Details of imputation methods are described under [section 8.6.2](#).

7.2.2 Handling of missing or incomplete dates

Imputation rules for missing AE start date:

Analyses of adverse events will assume that any AE with a missing start date is treatment emergent. Partial AE start dates are not allowed in the database.

Imputation rules for missing or partial medication start/stop dates are defined below:

Missing or partial medication start date:

- If the start date is completely missing, then the medication will be classified as ‘concomitant’.
- If the start date is partially missing then it will be compared to the partial portion of the date of first dose. If the partial medication start date is greater than the

partial portion of the first dose date and the medication is ongoing, the particular medication will be classified as ‘concomitant’.

Missing or partial medication stop date:

- If the stop date is completely missing then it will be assumed to be ongoing
- If the stop date is partially missing then it will be compared to the partial portion of the date of first dose. If the partial medication stop date is greater than the partial portion of the first dose date, the particular medication will be classified as ‘concomitant’.

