6.5.2.1 Adverse Events

6.5.2.1.1 Definition of Adverse Event

An adverse event is any untoward medical occurrence in a patient or clinical investigation subject administered a medicinal product and that does not necessarily have to have a causal relationship with this treatment. An adverse event can therefore be any unfavorable and unintended sign (including an abnormal laboratory finding, for example), symptom, or disease temporally associated with the use of a medicinal product, whether or not considered related to the medicinal product.

In this study, adverse events will be captured from the time a patient signs the ICF to the Follow-up Visit and include the following:

- Any new sign, symptom, or disease;
- Any new clinically significant or symptomatic laboratory/diagnostic test abnormality;
- Any clinically significant worsening of laboratory/diagnostic test abnormality;
- Any worsening (ie, clinically significant change in frequency, nature and/or intensity) of a pre-existing condition.

A pre-existing condition is a condition that is present prior to signing the ICF for the study. Pre-existing conditions, such as illnesses, symptoms, reactions, progression of disease states, and other comorbidities, as well as pre-existing laboratory/diagnostic test abnormalities, will be documented in the patient's record as medical history.

Signs and symptoms will be reported individually as adverse events (non-serious), unless a medical diagnosis was provided. Medical diagnosis, whenever provided, will be reported rather than individual signs and symptoms.

Any adverse event that satisfies any of the seriousness criteria described in [Section 6.5.2.1.3](#) will be reported as a serious adverse event (SAE) using the SAE Report Form, in addition to documenting in the eCRF.

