6.5.2.1.6 Adverse Event Documentation and Follow-up

All adverse events, including observed, elicited, or volunteered problems, complaints, or symptoms are to be recorded on the adverse event page in the patient’s eCRF from the time the patient signs the ICF until the Follow-up Visit/early termination, whether or not judged by the Investigator to be related to study drug. The need to capture this information is not dependent upon whether adverse events are related to study drug. Serious adverse events that occurred up to 30 days after the last dose of study drug need to be documented on an SAE Report Form if they are deemed by the Investigator to be “Related” to study drug.

Each adverse event is to be documented with a verbatim/reported term, start and stop date, severity, causal relationship to study drug, action taken with study drug, and outcome (resolved, resolved with sequelae, resolving, not resolved, fatal, unknown). The Investigator must review new adverse events and the outcome of ongoing adverse events frequently throughout the study.

In addition to recording all adverse events (serious and non-serious) in the patient’s eCRF, all SAEs must also be documented on the SAE Report Form for the study.

The Investigator will follow all adverse events until they resolve, the Investigator assesses them to be stable, or the patient’s participation in the study ends, whichever comes first. In addition, the Investigator will follow all adverse events assessed as related to study drug that are ongoing at the time of the patient’s last visit, until they resolve or the Investigator assesses them as stable, even if the patient’s participation in the study has ended. Resolution of such events is to be documented in the patient’s record as appropriate.

It is anticipated that some patients may undergo procedures and/or experience events that are common in the study population under investigation, independent of study therapy. Preplanned procedures and procedures (eg, kidney transplant or catheter replacement) or events that are independent of study therapy, according to the Investigator’s assessment, will be documented as specified in the Safety Management Plan.

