8 STATISTICAL METHODS

8.1 General statistical conventions

All statistical procedures will be completed using SAS version 9.2 or higher.

Unless otherwise noted, continuous variables will be summarized using descriptive statistics, including number of patients with non-missing observation (n), mean, median, standard deviation (SD), minimum (min) and maximum (max). Means and medians will be reported to one decimal place more than the raw data. Standard deviation will be reported to two more decimal places than the raw value. The minimum and maximum will be reported to the same decimal as the raw data.

Categorical variables will be summarized using the frequency count and the percentage of patients in each category. All percentages will be rounded to one decimal point. The number and percentage of patients will always be presented in the form XX (XX.X%) where the percentage is in parentheses. To ensure completeness, all summaries for categorical and discrete variables will include all categories, even if none of the patients in a particular category. Counts of zero in any category will be presented as “0”. Unless otherwise noted, for all percentages, the number of patients in the analysis population for the treatment group will be the denominator.

“Baseline” will be defined as per [section 7.1](#). For efficacy endpoints, “on-treatment” is defined as any assessment following the first dose of study drug and within 2 days from the last dose of study drug recorded in the patient diary. For safety endpoints (excluding adverse events), any assessment within 7 days after last dose of study drug will be deemed “on-treatment”. For all endpoints “End of treatment” (EOT), in summaries, will be represented by the last non-missing on-treatment value recorded up to and including the Week 12/Early Termination visit. Treatment emergence for adverse events is described in [section 8.7.1](#). Summaries will be presented across all scheduled visits and EOT unless stated otherwise. Only on-treatment data will be used in summaries and statistical analyses (with the exception of the Patient Global Impression of Change).

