8.7.1 Adverse events

All adverse events (AE) will be coded using MedDRA dictionary to the corresponding MedDRA system organ class (SOC) and Preferred Term (PT) for standardization and summary purposes. Only treatment emergent adverse events (TEAEs) will be included in summary tables, except for a table presenting an overall summary of all AES and of REAEs. Summaries will provide results overall and by treatment.

TEAEs are defined as adverse events (AEs) with an onset date on or after the first dose of the study drug up to the End of Treatment/Early Termination visit or 7 days after the last dose, whichever is later.

The incidence of TEAEs will be presented using counts and percentages of patients with adverse events and tabulated by SOC and preferred term. System organ class will be sorted alphabetically and preferred term within SOC will be sorted by descending frequency based on the incidence across all patients in the safety population. A patient will be counted only once in the incidence count for a MedDRA SOC or preferred term, although a patient may have multiple occurrences (start and stop) of an event associated with a specific MedDRA preferred term or SOC.

The following specific summary tables will be generated:

- An overall summary showing the number and percentage of patients with
 - Any AE (both TEAE and non-TEAE)
 - TEAE
 - Serious TEAE
 - Serious non-TEAE
 - Related TEAE
 - Severe TEAE
 - TEAE leading to drug interruption
 - TEAE leading to dose reduction
 - TEAE leading to study drug discontinuation
 - Number of any events and number of TEAEs (Count only)
- TEAEs by SOC and preferred term
- TEAEs related to study drug by SOC and preferred term
- TEAEs by SOC, preferred term and maximum severity
- TEAEs occurring in $\geq 5\%$ of patients in at least 1 treatment group
- Treatment-related TEAEs occurring in $\geq 5\%$ of patients in at least 1 treatment group

Statistical Analysis Plan (SAP)

- Serious TEAEs by SOC and preferred term
- TEAEs leading to study drug discontinuation by SOC and preferred term

If the relationship to the study drug of an adverse event (AE) is missing, the AE will be categorized as “related” to the study drug. If a patient reports 2 or more AEs that code to the same preferred term, the event with the maximum relationship will be included in the table.

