If the severity to the study drug of an AE is missing, the AE will be categorized as “severe”. If a patient reports 2 or more adverse events that code to the same preferred term, the event with the maximum severity will be included in the table.

All adverse events will be listed in chronological order, including patient identifier, age, race, gender, a flag indicating whether the event was treatment-emergent, and all related event status information (start and stop dates, whether the event was ongoing, study day of onset, severity, seriousness, relationship to study drug, action taken with study drug, and outcome).

In addition, separate listings will be generated for serious adverse events (SAEs), deaths, and adverse events leading to study drug discontinuation.

A coding list of SOC, high level, preferred and lowest level terms and the verbatim text associated with them will also be produced additionally. TEAEs and non-TEAEs will be listed separately.

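### SAP 7.2.2 has no stop-date exception, so an adverse event that ended before the first dose but lacks a start date would be counted as treatment emergent

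*SAP*

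**What the plan says.** SAP 7.2.2 states the rule for adverse events: "Analyses of adverse events will assume that any AE with a missing start date is treatment emergent". It adds: "Partial AE start dates are not allowed in the database". No condition is attached to either sentence, and the stop date of the event is not mentioned.

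SAP 8.1 says "Treatment emergence for adverse events is described in" section 8.7.1. That section defines treatment-emergent events (TEAEs) as "adverse events (AEs) with an onset date on or after the first dose of the study drug", up to the later of the end-of-treatment or early-termination visit and 7 days after the last dose. It too has no rule based on the stop date. Apart from one overall table, the SAP 8.7.1 summary tables contain TEAEs only.

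On collection, Protocol 6.5.2.1.1 says that "adverse events will be captured from the time a patient signs the ICF to the Follow-up Visit", and screening may begin as early as Day -28. Protocol 6.5.2.1.6 requires: "Each adverse event is to be documented with a verbatim/reported term, start and stop date, severity", among other items. The SAP 8.7.1 listings carry "start and stop dates, whether the event was ongoing".

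**The concern.** Events are collected before dosing, so some will begin and end in screening or run-in. If such an event has a stop date but no start date, the stop date alone settles its timing. The SAP rule does not use it, and puts the event among those that emerged on treatment.

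What is at stake is the accuracy of the TEAE tables in that situation. The same classification feeds the interim safety summaries in SAP 8.9.2.5, at the analysis where a dose found unsafe or poorly tolerated is to be dropped (SAP 8.9). A worst-case default makes sense when timing is unknown. In this subset it is known.

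**Working it through.** The plan has no figure to reproduce here. The check is a comparison of two rules, followed by simple proportions for scale.

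**1. The two rules applied to one record.** Take an event with a missing start date and a complete stop date before the first dose.

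- Onset cannot be later than stop, so onset ≤ stop < first dose.
- Under SAP 8.7.1, which needs an event "with an onset date on or after the first dose of the study drug", the record is not a TEAE.
- Under SAP 7.2.2 it is a TEAE, because the start date is missing and nothing else is asked.

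The two sections give opposite answers for this record.

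**2. Where they do not conflict.** If the stop date is missing, the event is ongoing, or the stop date is on or after the first dose, onset may have been before or after dosing. The default then fills a gap in the definition and cannot be shown to contradict it.

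**3. Search for an exception.** None was found in SAP 7.2.2, 8.1, 8.7.1, 8.9.2.5 or section 9 (changes from the protocol), nor in Protocol 8.7.2. For medications, SAP 7.2.2 does compare a partially missing stop date with the date of first dose. It has no counterpart for adverse events.

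**4. Scale of one misclassified patient.** Inputs: 60 per arm planned and 120 per arm at most (SAP 5); interim at 50-60% of 240 patients (SAP 8.9); 1:1:1:1 allocation, assumed to give equal arms.

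| Setting | Patients per arm | Weight of one patient |
|---|---|---|
| Final, planned size | 60 | 1/60 = 1.7 points |
| Final, maximum size | 120 | 1/120 = 0.8 points |
| Interim, 50% | 0.50 × 240 / 4 = 30 | 1/30 = 3.3 points |
| Interim, 60% | 0.60 × 240 / 4 = 36 | 1/36 = 2.8 points |

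SAP 8.7.1 has tables of terms that reach 5% in at least one arm. With 60 per arm, one added patient takes a term from 2/60 = 3.3% to 3/60 = 5.0%, which brings it into those tables.

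These figures are the weight of any single patient. They do not estimate how often the misclassification would happen.

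**The case against.** The strongest case against the point is that it is immaterial.

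- The record needs three things together: no start date, a recorded stop date, and a stop before the first dose. The protocol requires a start date for every event (6.5.2.1.6), applies database checks (9.3) and source data verification (11.0), and treats conditions present before consent as medical history (6.5.2.1.1).
- Classing a missing onset as treatment emergent matches the plan's other worst-case defaults: missing relatedness becomes related, and missing severity becomes severe (SAP 8.7.1).
- Safety analysis is descriptive (Protocol 8.7), the rule is the same in every arm, and it overcounts events and hides none. A patient counts once per term, so one who also has that term on treatment adds nothing.
- Listings show the stop date, so a reader of the listing could spot the record. The interim package includes an adverse event listing.

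All of this stands, and it keeps the point minor. It does not remove it, because a default for unknown timing is being applied where the timing is known.

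A reader might infer more than the documents support:

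- *That the SAP knowingly overrides the stop date.* It is silent on stop dates for adverse events. This is an omitted exception.
- *That the ban on partial start dates turns events with a known month but unknown day into missing ones.* Nothing says so. The ban may equally mean that sites must resolve a full date.
- *That the tables of related events are inflated.* An event that ended before any dose would reach them only if it was also called related or had no relatedness recorded.
- *That a real difference between arms is masked.* No frequency is given, and no such effect has been shown.

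**Conclusion.** The point holds in a narrow form. SAP 7.2.2, as written, counts as treatment emergent an adverse event with no start date that is recorded as ending before the first dose, and SAP 8.7.1 cannot admit that event. For every other missing start date the rule is a sensible conservative default and should stay.

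It is a minor point: worth correcting, but no threat to the trial's conclusions. The effect per patient is 1.7 points on a term at 60 per arm, 0.8 at 120, and 2.8 to 3.3 at the interim. The total effect cannot be stated, because the documents do not say how many such records exist. It is probably very small.

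The conclusion assumes that the recorded stop date is correct and that the programming follows the SAP text literally. The interim figures also assume equal arms.

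**What to change.** Amend the adverse event rule in SAP 7.2.2 to read along these lines:

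> An AE with a missing start date is treatment emergent unless its stop date (complete or partial) shows that it ended before the first dose.

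Add a cross-reference from SAP 8.7.1, so that the definition and the missing-date rule are read together. A partial stop date should exclude an event only when the known part is enough to place the end before dosing. An event that stopped on the day of first dose stays treatment emergent.

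The cost is one SAP sentence, one cross-reference and one programming condition. No information is lost: the excluded event still counts in the any-AE row of the overall summary, in the serious non-TEAE row if it was serious, and in the listings.

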7.3 Assessment Time Windows

For the primary analysis variable, assessment time windows are not needed since the NRS Itch Intensity Assessments Log collects the daily individual scores and average NRS score for the run-in and each post-baseline visit week are calculated based on these daily scores.

Assessments collected by study week that are collected at early termination visits and unscheduled visits will be assigned to a post-baseline planned visit window, if the early termination or unscheduled visit day falls between +/- 2 days of the planned visit. Should more than one measurement fall within a visit window, priority is given first to the measurement with a non-missing value in the following order, first the scheduled assessment, second to an early termination visit, then the unscheduled assessment closest to the planned day will be used. In the case that two unscheduled visits are equidistant, the latest will be used. This rule will be applied both to efficacy and safety endpoints.

8 STATISTICAL METHODS

8.1 General statistical conventions

All statistical procedures will be completed using SAS version 9.2 or higher.

Unless otherwise noted, continuous variables will be summarized using descriptive statistics, including number of patients with non-missing observation (n), mean, median, standard deviation (SD), minimum (min) and maximum (max). Means and medians will be reported to one decimal place more than the raw data. Standard deviation will be reported to two more decimal places than the raw value. The minimum and maximum will be reported to the same decimal as the raw data.

Categorical variables will be summarized using the frequency count and the percentage of patients in each category. All percentages will be rounded to one decimal point. The number and percentage of patients will always be presented in the form XX (XX.X%) where the percentage is in parentheses. To ensure completeness, all summaries for categorical and discrete variables will include all categories, even if none of the patients in a particular category. Counts of zero in any category will be presented as “0”. Unless otherwise noted, for all percentages, the number of patients in the analysis population for the treatment group will be the denominator.

“Baseline” will be defined as per [section 7.1](#). For efficacy endpoints, “on-treatment” is defined as any assessment following the first dose of study drug and within 2 days from the last dose of study drug recorded in the patient diary. For safety endpoints (excluding adverse events), any assessment within 7 days after last dose of study drug will be deemed “on-treatment”. For all endpoints “End of treatment” (EOT), in summaries, will be represented by the last non-missing on-treatment value recorded up to and including the Week 12/Early Termination visit. Treatment emergence for adverse events is described in [section 8.7.1](#). Summaries will be presented across all scheduled visits and EOT unless stated otherwise. Only on-treatment data will be used in summaries and statistical analyses (with the exception of the Patient Global Impression of Change).

Unless otherwise stated, all statistical testing will be two-sided and will be performed using a significance (alpha) level of 0.05. Two-sided 95% confidence intervals (CI) will be provided appropriately. For tests of hypothesis of treatment group differences, the associated p-value will be reported. All p-values will be rounded to three decimal places; p-values that round to 0.000 will be presented as “< 0.001”.

All patients data, including those derived, will be presented in individual patient data listings. Unless otherwise stated, unscheduled visit results will be included in date/time chronological order, within patient listings only. All listings will be sorted by treatment, patient number, date/time and visit. Patient listings of efficacy and safety data will be presented for all full analysis set and safety set patients respectively unless specified otherwise.

